5.1 ALSFRS-R

The definitions of ALSFRS-R scores are the same as described in the M-SAP with the clarification that scores will be considered missing in cases of item nonresponse. Pre-baseline slope in ALSFRS-R (delta-FRS) is defined as 48 minus the baseline ALSFRS-R total score then divided by the number of months from onset of symptomatic weakness to the Baseline Visit. The number of months will be calculated as the difference in days from onset of symptomatic weakness to the Baseline Visit multiplied by 12 / 365.25. The date of onset of symptomatic weakness will be imputed as the fifteenth day of a month if not specified more precisely.

5.2 SVC

The derivation of SVC percent-predicted of normal is the same as described in the M-SAP with age calculated as number of days from date of birth to the date of a given SVC assessment divided by 365.25 and with the following correspondence between self-identified race and race defined by Global Lung Initiative (GLI) classification:

Self-identified Race	GLI-defined Race
American Indian or Alaska Native	Mixed/Other
Asian	South East Asian
Black or African American	African American
Native Hawaiian or Other Pacific Islander	Mixed/Other
White	Caucasian
Unknown	Caucasian
Not reported	Caucasian
More than one race indicated	Mixed/Other

5.3 Home Spirometry

Home spirometry assesses FVC remotely using a smartphone app (ZEPHYRx, Albany, NY) and a handheld spirometer (Spirobank Smart, Medical International Research, Rome, Italy). Coordinators guide participants through 3 to 8 maneuvers with live-video coaching using the ZEPHYRx platform. Flow loops are classified for acceptability and repeatability using American Thoracic Society (ATS) criteria and are manually reviewed by the NEALS Outcomes Center (Barrow Neurological Institute, Phoenix, AZ). The maximum acceptable FVC is converted to percent of predicted normal using GLI norms based on sex, age at time of assessment, height at time of screening, and race. Higher values indicate greater respiratory function.

5.4 HHD and Grip Strength

The derivation of HHD upper and lower extremity scores and HHD0 are the same as described in the M-SAP with the revision that HHD0 is a composite endpoint with death or death equivalent.

A second HHD time-to-event endpoint is defined as the time from the Baseline Visit to the second post-baseline occurrence of a muscle with a strength recording of 0 among those muscles that were non-zero at baseline, or time to death or death equivalent, whichever occurs first (HHD0²).

Time at risk for HHD0 and HHD0² will be censored at the Week 24 Visit, if completed, the date of consent withdrawal, if withdrawn, or the last date at which vital status is known prior to the end of the Week 24 Visit window for participants lost to follow-up.

HHD global average percentage, HHD0, and HHD0² are measures of the secondary endpoint HHD and grip strength.

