6.1.10 Process for Early Terminations

A research participant may choose to discontinue their participation at any time for any reason. The SI or designee will encourage the participant to follow the study protocol under intent-to-treat principle and follow the study visits, off treatment, up to the week 24 visit. If a participant decides to discontinue IP, but will complete the protocol, an in-person Early Termination Visit and Follow-Up Safety Call is not necessary.

Participants who early terminate from the study and do not complete the protocol will be asked to be seen for an in-person Early Termination Visit and complete a Follow-Up Safety Call. If a participant is not able to be seen in-person, safety assessments and others that can be conducted remotely should be performed.

The in-person Early Termination Visit should be scheduled as soon as possible after a participant early terminates. If the participant early terminates during the placebo-controlled portion of the Regimen, all assessments that are collected at the Week 24 in-clinic visit should be conducted. If the participant early terminates during the OLE period, all assessments that are intended for collection at the OLE Week 24 in-clinic visit should be conducted. The Follow-Up Safety Call should be completed approximately 28 days after the last dose of IP.

If the Early Termination Visit occurs approximately 28 ± 3 days after the last dose of IP, the information for the Follow-Up Safety Call can be collected during the Early Termination Visit, and a separate Follow-Up Safety Call does not need to be completed. If the in-person Early Termination Visit does not occur within 28 ± 3 days of the last dose of IP, the Follow-Up Safety Call should occur approximately 28 ± 3 days after the last dose of IP and the Early Termination Visit will be completed after the Follow-Up Safety Call.

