2.9 RGD Schedule of Activities (SoA)

Activity	MP Scrn ¹	RGD Scrn ¹	Base-line	Week 2	Week 4 ¹⁴	Week 8 ¹⁹	Week 12	Week 16 ¹⁹	Week 20	Week 24/E T ^{14, 22}	Final Call ¹¹
	Clinic	Clinic	Clinic	Phone	Clinic	Clinic	Phone	Clinic	Phone	Clinic	Phone
	-42d to -1d	-41d to 0d	Day 0	Day 14 ±3	Day 28 ±7	Day 56 ±7	Day 84 ±3	Day 112 ±7	Day 140 ±3	Day 168 ±7	28d ±3 ALD
Written Informed Consent ²	X	X									
Inclusion/Exclusion Review	X	X ³									
ALS & Medical History	X										
Demographics	X										
Physical Examination	X										
Neurological Exam	X										
Vital Signs ⁴	X		X		X	X		X		X	
Slow Vital Capacity	X ²⁰		X			X		X		X	
Home Spirometry	X ²⁰		X			X		X		X	
Muscle Strength Assessment			X			X		X		X	
ALSFRS-R	X		X		X	X	X	X	X	X	
ALSAQ-40			X							X	
CNS Bulbar Function Scale			X			X		X		X	
CNS Lability Scale			X			X		X		X	
12-Lead ECG	X	X ¹⁵	X ¹⁶		X ¹⁶					X ^{15, 16, 17}	

Activity	MP Scrn ¹	RGD Scrn ¹	Base-line	Week 2	Week 4 ⁴	Week 8 ¹⁹	Week 12	Week 16 ¹⁹	Week 20	Week 24/E T ^{14, 22}	Final Call ¹¹
	Clinic	Clinic	Clinic	Phone	Clinic	Clinic	Phone	Clinic	Phone	Clinic	Phone
	-42d to -1d	-41d to 0d	Day 0	Day 14 ±3	Day 28 ±7	Day 56 ±7	Day 84 ±3	Day 112 ±7	Day 140 ±3	Day 168 ±7	28d ±3 ALD
Clinical Safety Labs ^{5, 21}	X		X		X	X		X		X	
Biomarker Blood Collection ²¹			X			X		X		X	
Plasma PK collection ²¹					X					X	
Biomarker Urine Collection			X			X		X		X	
DNA Collection ^{7, 21} (optional)			X								
CSF Collection (optional)			X					X ¹³			
Concomitant Medication Review	X	X	X	X	X	X	X	X	X	X	
Adverse Event Review ⁶	X	X	X	X	X	X	X	X	X	X	X
Suicidality C-SSRS			X		X	X		X		X	
Install Smartphone App ²³			X								
Voice Recording ⁹			X		X	X		X		X	
Uninstall Smartphone App										X	
Randomization to Regimen	X										
Randomization within Regimen			X								
Administer/Dispense Study Drug			X ⁸		X ¹⁸	X		X		X ^{10, 18}	
Drug Accountability/Compliance				X ²⁴	X	X	X ²⁴	X	X ²⁴	X	
Exit Questionnaire										X	
Vital Status Determination ¹²										X	

Abbreviations: ALD = after last dose, ALS = amyotrophic lateral sclerosis, ALSAQ-40 = ALS Assessment Questionnaire, ALSFRS-R = ALS Functional Rating Scale Revised, CSF = cerebrospinal fluid, C-SSRS = Columbia-Suicide Severity Rating Scale, d = day, DNA = deoxyribonucleic acid, ECG = electrocardiogram, MP = Master Protocol, RGD = the pridopidine regimen, Scrn = Screening Visit.

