¹ Master Protocol Screening procedures must be completed within 42 days to 1 day prior to the Baseline Visit. The Regimen-Specific Screening Visit and Baseline Visit should be combined, if possible.

² During the Master Protocol Screening Visit, participants will be consented via the Platform Trial informed consent form (ICF). After a participant is randomized to a regimen, participants will be consented a second time via the regimen-specific ICF.

³ At the Regimen Specific Screening Visit, participants will have regimen-specific eligibility criteria assessed.

⁴ Vital signs include weight, systolic and diastolic pressure, respiratory rate, heart rate and temperature. Height measured at Master Protocol Screening Visit only.

⁵ Clinical safety labs include hematology (CBC with differential), complete chemistry panel, thyroid function and urinalysis. Serum pregnancy testing will occur in women of child-bearing potential at the Master Protocol Screening Visit and as necessary during the study. Pregnancy testing is only repeated as applicable if there is a concern for pregnancy.

⁶ Adverse events that occur after signing the master protocol consent form will be recorded.

- ⁷ The DNA sample can be collected after Baseline Visit if a baseline sample is not obtained or the sample is not usable.
- ⁸ Administer first dose of IP only after Baseline Visit procedures are completed, except for the post-dose ECG.
- ⁹ In addition to study visits outlined in the SOA, participants will be asked to complete twice weekly voice recordings at home.
- ¹⁰ Drug will only be dispensed at this visit if the participant continues in the OLE.
- ¹¹ Participants will only have a Follow-Up Safety Call at this time if they *do not* continue on in the OLE. Participants who continue into OLE will have a Follow-Up Safety Call after their last dose of IP during the OLE period.
- ¹² Vital status, defined as a determination of date of death or death equivalent or date last known alive, will be determined for each randomized participant at the end of the placebo-controlled portion of their follow-up (generally the Week 24 Visit, as indicated). If at that time the participant is alive, his or her vital status should be determined again at the time of the last participant's last visit (LPLV) of the placebo-controlled portion of a given regimen. We may also ascertain vital status at later time points by using publicly available data sources as described in section 8.15 of the Master Protocol.

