5.12 Hospitalization and Other Clinical Events

Times to the following clinically relevant events are defined:

- Time to first hospitalization due to a serious adverse event (SAE),
- Time to first hospitalization due to an ALS-related SAE,
- Time to first use of assisted ventilation,

- Time to first placement of a feeding tube,
- Time to King's stage 4a or 4b, and
- Time to first instance of hospitalization for an SAE, feeding tube placement, tracheostomy, initiation of PAV, or death.

Time at risk for each event will be measured from each participant's Baseline Visit. Time to first hospitalization excludes hospitalizations for elective procedures. ALS-related SAEs are those indicated as related to ALS disease progression by the site investigator. Participants who are already using assisted ventilation or have a feeding tube at the time of the Baseline Visit will be excluded from analysis of those endpoints. Death or death equivalent will be considered an outcome for each of the events listed, forming a composite endpoint.

Time at risk for these events will be censored at the Week 24 Visit, if completed, the date of consent withdrawal, if withdrawn, or the last date at which the status of each endpoint is known prior to the end of the Week 24 Visit window for participants lost to follow-up. Time to King's stage 4a or 4b is interval censored between ALSFRS-R assessments.

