6.5.8 HHD0 and HHD0²

Analyses of HHD0 are the same as specified in the M-SAP with the addition of parallel analyses of HHD0², with a separate analysis that includes baseline serum NfL level as an additional covariate, and with the clarification that time to zero strength for both analyses is interval censored between HHD assessments.

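### The SAP censors HHD0 and HHD0² for participants lost to follow-up at last known vital status, although zero strength can be seen only at an HHD assessment, and this rule is not reconciled with SAP 5.12 or 6.5.8

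*SAP*

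**What the plan says.** - **Endpoint.** SAP 5.4 states that "HHD0 is a composite endpoint with death or death equivalent". HHD0² is the second occurrence of a zero reading, or death or death equivalent if that comes first.
- **Censoring.** SAP 5.4 ends time at risk for both endpoints at the Week 24 Visit if completed, at consent withdrawal, or, for those lost, at "the last date at which vital status is known prior to the end of the Week 24 Visit window for participants lost to follow-up".
- **Comparable events.** SAP 5.12 covers other clinical events that are also composites with death or death equivalent. For participants lost to follow-up it uses "the last date at which the status of each endpoint is known prior to the end of the Week 24 Visit window".
- **Analysis.** SAP 6.5.8 adds that "time to zero strength for both analyses is interval censored between HHD assessments". Otherwise it refers to the Master SAP.
- **Measurement.** In SAP 2.9 the row "Muscle Strength Assessment" is marked at Baseline and Weeks 8, 16 and 24.
- **Vital status.** Footnote 12 of the same schedule says that it "will be determined for each randomized participant at the end of the placebo-controlled portion of their follow-up", and again at the last participant's last visit for those still alive. It adds: "We may also ascertain vital status at later time points by using publicly available data sources".
- **Early termination.** Protocol 6.1.10 says that "all assessments that are collected at the Week 24 in-clinic visit should be conducted" when a participant terminates early in the placebo-controlled period.

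**The concern.** A zero reading needs a dynamometer. Someone last tested at Week 8 (Day 56) and known to be alive at Week 24 (Day 168) adds 168 − 56 = 112 days at risk, during which the death component could be observed but the zero-strength component could not. Treating those days as free of zero strength understates the HHD0 risk. If the arms lose different proportions, the arm with more loss looks better even when the drug does nothing.

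Two other clauses of 5.4 leave a similar gap. Consent may be withdrawn some time after the last HHD, and the Week 24 Visit may be completed without HHD.

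**Working it through.** The plan states no HHD0 event rate, loss rate or power, so there is no figure to reproduce. The check asks how far the literal 5.4 rule moves the estimate.

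**Inputs.** From the documents: HHD every 8 weeks, a composite with death, and the two candidate censoring dates. Assumed: 24-week zero-strength risk *r* of 10%, 20% or 40%; 24-week death risk *d* of 5%; loss of HHD follow-up *L* of 10% to 30%, non-informative and occurring just after the Baseline, Week 8 or Week 16 assessment; vital status known to Week 24.

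**Formulas, per 8-week interval.**
- Zero strength: z = 1 − (1 − r)^(1/3)
- Death: m = 1 − (1 − d)^(1/3)
- Composite: c = 1 − (1 − z)(1 − m)
- Loss: l = 1 − (1 − L)^(1/3)

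Followed participants have events at rate c. Lost participants stay in the risk set under 5.4 but can have an event only by dying, at rate m. Interval risk is q = (followed × c + lost × m) / (followed + lost).

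**Worked case: r = 20%, d = 5%, L = 20%.** True composite risk is 1 − 0.80 × 0.95 = 24.0%. Here z = 0.0717, m = 0.0170, c = 0.0874 and l = 0.0717.

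| Weeks | Followed | Lost, still counted | At risk | Events | q | Event-free at end |
|---|---|---|---|---|---|---|
| 0–8 | 0.9283 | 0.0717 | 1.0000 | 0.0824 | 0.0824 | 0.9176 |
| 8–16 | 0.7864 | 0.1312 | 0.9176 | 0.0710 | 0.0773 | 0.8467 |
| 16–24 | 0.6662 | 0.1804 | 0.8467 | 0.0613 | 0.0724 | 0.7854 |

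The estimated risk is 1 − 0.7854 = 21.5%, against a true 24.0%.

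**Other loss levels, 5.4 read literally.**

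| True composite risk | 10% loss | 20% loss | 30% loss |
|---|---|---|---|
| 24.0% (r = 20%) | 22.7% | 21.5% | 20.1% |
| 43.0% (r = 40%) | 40.6% | 38.1% | 35.5% |

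Removing lost participants from the risk set at their last HHD returns 24.0% and 43.0% at every loss level.

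**Does 6.5.8 remove the bias?** Not if the 5.4 date stays as the right bound. An interval-censored exponential fit to 200,000 simulated participants per scenario gave 22.7%, 21.5% and 20.2% at 10%, 20% and 30% loss, against a true 24.0%.

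**Between arms, no true effect.** The ratio is taken as events divided by intervals at risk. For r = 20% with 20% versus 10% loss: (0.2146 / 2.7643) / (0.2275 / 2.7546) = 0.0776 / 0.0826 = 0.94.

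| Loss, active vs placebo | r = 10% | r = 20% | r = 40% |
|---|---|---|---|
| Equal | 1.00 | 1.00 | 1.00 |
| 20% vs 10% | 0.95 | 0.94 | 0.93 |
| 30% vs 10% | 0.90 | 0.88 | 0.86 |

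In the last row, with 120 active and an assumed 160 placebo participants (40 from each of four regimens), a nominal 5% two-sided test would reject in about 6%, 8% and 12% of trials.

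**Shorter gap.** If vital status runs only about 4 weeks past the last HHD, r = 20% with 20% loss gives 23.3% instead of 24.0%. The ratio at 20% versus 10% loss is 0.98.

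**Deaths after the last HHD.** If survivors are censored at the last HHD but every later death still counts, the fit overshoots: 24.1%, 24.6% and 24.9% against 24.0% at 10%, 20% and 30% loss. For r = 10% at 30% loss it gives 15.5% against a true 14.5%. Counting deaths only up to 8 weeks after the last HHD reduces this to 24.0%, 24.3% and 24.4%, and to 15.0% in the r = 10% case.

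**The case against.** The best defence is that 5.4 sets time at risk for a composite, and last known vital status is the right bound for its death component. Section 6.5.8 could then be read as treating a participant who is never retested as known to be free of zero strength only up to the last HHD. The underlying HHD0 analysis is in the Master SAP, which was not available, and it may say how such participants enter the likelihood.

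Part of this stands. The literal reading is not the only one, and a reader should not infer that lost participants will certainly be analysed as free of zero strength. But 6.5.8 speaks of time between assessments and is silent on time after the last one, where 5.4 does give a date. SAP section 1 also places this SAP above the Master SAP where they differ. The death component does not explain the wording either, since the 5.12 endpoints are composites with death too.

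Other limits also stand:
- Early terminators are asked to attend a visit with all Week 24 assessments, so the affected group may be small.
- Public records are mentioned only as a possibility at later time points, not as a routine source of in-window dates.
- Section 5.12 also censors at a completed Week 24 Visit, so copying its wording would not cover a visit without HHD.

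A reader might infer that the rule favours pridopidine, or that loss related to progression makes it worse. The documents support neither. They give no loss by arm, and the direction reverses if placebo loses more. Informative loss is neither quantified in the documents nor cured by censoring at the last HHD.

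**Conclusion.** The point holds as a stated censoring date that does not fit the zero-strength component and is left unreconciled with two other sections. Applied literally, it understates composite risk by 1.3, 2.5 and 3.9 percentage points (24.0% less 22.7%, 21.5% and 20.1%) at 10%, 20% and 30% loss. A false difference between arms needs unequal loss and is modest: 0.93 to 0.95 at 20% versus 10%, close to 1 when the gap to vital status is short, and 1.00 when loss is equal.

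All these sizes rest on assumed event and loss rates, non-informative loss and, except for the short-gap case, vital status known to Week 24.

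Severity is minor to moderate. SAP 4.2 lists HHD0 and HHD0² as exploratory, although 5.4 calls them measures of a secondary endpoint. Neither is among the five hierarchical endpoints in 6.5.1, and the primary analysis does not use them.

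**What to change.** In SAP 5.4:

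1. Set the right-censoring bound for the zero-strength component at the last date on which HHD was assessed. Apply this to loss to follow-up, to consent withdrawal, and to a Week 24 Visit completed without HHD.
2. Align the wording with the endpoint-status principle in 5.12, and say in 6.5.8 that the last HHD is the left bound for anyone not retested.
3. State how deaths and death equivalents after the last HHD enter the composite, so that follow-up after that date does not count only for those who die. Options are an illness-death model with interval censoring, or counting such deaths only within a set window after the last HHD. The window is simpler but, as shown above, leaves a small overshoot.

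This needs no new data. The cost is a few sentences of SAP text, slightly less follow-up time and slightly wider intervals for the two endpoints. The illness-death option also adds programming.

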5.5 Quantitative Voice Characteristics

Voice samples will be collected using the Aural Analytics app installed on either an Android or iOS-based smartphone. At each assessment, participants perform a set of speaking tasks: reading 5 prespecified sentences, reading 5 sentences chosen at random from a large sentence bank, repeating a consonant-vowel sequence, producing a sustained phonation, and counting on a single breath. Speech analysis will be performed by Aural Analytics to derive the following quantitative voice characteristics: maximum phonation time, pause rate, breathy vocal quality, pitch instability, regulation of voicing, articulatory precision, speaking rate, articulation rate, and monotonicity. Aural Analytics will use data on quantitative voice characteristics and participant age, sex, race, height, and weight to derive a prediction of vital capacity at the Baseline Visit.

5.6 Biofluid Biomarkers of Neurodegeneration

Blood biomarkers of neurodegeneration, including biomarkers of neuromuscular dysfunction, will be assayed. These will include serum creatinine and serum and CSF neurofilament light chain (NfL). Serum creatinine will be assayed by the kinetic Jaffe method (test 001370, Labcorp, Burlington, NC). NfL will be assayed by single-molecule array (Simoa; Quanterix, Billerica, MA). Levels of serum and CSF NfL that are reported to be below the limit of quantitation will be imputed at the limit of quantitation. Levels of serum and CSF NfL will be log-transformed in all analyses.

5.7 ALSAQ-40

The description of the ALSAQ-40 instrument and item-level scores are the same as described in the M-SAP. Each of the five domains will be scored as the mean of all domain-specific items multiplied by 25 (range 0 to 100). An overall symptom index (SI) will be scored as the mean of the five domain scores. A domain score will be missing if more than 20% of the items are missing; otherwise, item non-response will be mean-imputed from other completed items from the same assessment. The ALSAQ-40 SI will be missing if any domain scores are missing. Higher scores indicate worse quality of life.

5.8 CNS-BFS

The definition of CNS-BFS total score is the same as described in the M-SAP.

5.9 CNS-LS

The Center for Neurologic Study Lability Scale (CNS-LS, Moore et al. 1997) is a 7-item instrument completed by participants for assessing emotional lability. For each item, participants are asked to rate the perceived frequency at which they experienced a manifestation of pseudobulbar affect (PBA) over the past week on a scale from 1 ("Applies never") to 5 ("Applies most of the time"). The total score is the sum of all items (range 7 to 35). Higher scores indicate greater emotional lability. A CNS-LS score of 13 or higher may suggest PBA.

5.10 Survival

The primary definition of survival time is the same as described in the M-SAP with the clarifications that PAV is defined as more than 22 hours per day of noninvasive or invasive mechanical ventilation for more than seven consecutive days, that time at risk should not be censored at date of consent withdrawal, and that time at risk should be censored at date last known alive. The date of PAV initiation, where applicable, will be imputed as the fifteenth day of a month if not specified more precisely. Any participant on PAV at baseline will be censored at baseline. A secondary survival endpoint of death alone, independent of any death equivalent (including a death equivalent that occurs prior to baseline), is also defined and will be censored at the Week 24 Visit if completed or at the earlier of the end of the Week 24 Visit window or date last known alive if a Week 24 visit is not completed. An exploratory survival endpoint of death or death-equivalent will censor at the earlier of last known PAV-free or last known alive.

Time at risk for the composite endpoint of death or death equivalent and time at risk for the endpoint of death alone will be measured from each participant's Baseline Visit. Time at risk will be censored at two time points: (1) at the Week 24 Visit as defined in the M-SAP, and (2) at a subsequent assessment of death or death equivalent scheduled approximately at the end of placebo-controlled follow-up of the last RGD participant. The primary analysis of survival will evaluate PAV-free survival to the Week 24 Visit time point.

